## 9. STATISTICAL CONSIDERATIONS AND DATA ANALYSES

### 9.1. Hypotheses

The study is designed to demonstrate that the antiviral effect of switching to CAB LA + RPV LA (CAB) is non-inferior to continuation of current first line antiretroviral regimen (current ART) at Week 48 in HIV-1 infected ART-experienced participants. Non-inferiority in the proportion of participants with virologic failure at Week 48 (per FDA's snapshot algorithm for assessing HIV-1 RNA  $\geq 50$  copies/mL) can be concluded if the upper bound of a two-sided 95% confidence interval for the difference in failure rates between the two treatment arms (CAB – current ART) is not more than 6%.

If  $f_{la}$  is the failure rate for CAB LA + RPV LA and  $f_c$  is the failure rate for current ART then the hypotheses can be written as follows:

$$H_0: f_{la} - f_c \geq 6\% \quad H_1: f_{la} - f_c < 6\%$$

### 9.2. Sample Size Considerations

#### 9.2.1. Sample Size Assumptions

This study will randomize approximately 285 participants per arm. Assuming the true virologic failure rate is 3% for the CAB LA + RPV LA injectable regimen and 2% for current ART arm, a non-inferiority margin of 6%, and a 2.5% one-sided significance level, this would provide approximately 97% power to show non-inferiority for the proportion of participants with virologic failure (per FDA's snapshot algorithm for assessing HIV-1 RNA  $\geq 50$  copies/mL) at Week 48.

This sample size of 285 participants per arm will also provide at least 90% power to show non-inferiority in the proportion of participants with plasma HIV-1 RNA  $< 50$  c/mL (per FDA's snapshot algorithm) at Week 48 over a range of true response rates, on the basis of a -10% non-inferiority margin and 2.5% one-sided significance level (see [Table 13](#)). Assuming true response rates for the CAB LA + RPV LA arm and current ART arm are both 87%, the power is at least 94% to show non-inferiority for this key secondary endpoint.

In addition, the data from this study, together with data from a separate study, 201584 (FLAIR), will be combined to assess non-inferiority using a 4% non-inferiority margin. The combined sample size from both studies (570 pooled per arm) will provide 90% power, under the assumptions described above, to show non-inferiority for the proportion of participants with virologic failure (per FDA's snapshot algorithm for assessing HIV-1 RNA  $\geq 50$  c/mL) at Week 48.

### 9.2.1.1. Rationale for non-inferiority margin

The selection of the non-inferiority margins in a switch study comparing regimens (rather than individual component drugs) is exclusively informed by clinical judgment (and practical considerations) since regimen efficacy over placebo will be obvious – if the regimen efficacy were no better than placebo virtually all subjects would show virologic failure. While this implies that any non-inferiority margin would be justifiable statistically, it would not be justifiable clinically to accept more than a 4 to 6 percent increase in the rate of virologic failure relative to standard-of-care regimen(s).

The non-inferiority margin of 6% is chosen in consideration of the FDA's 2015 guidance document [FDA, 2015 \(Human Immunodeficiency Virus-1 Infection: Development of ART Drugs for Treatment, November 2015\)](#) which is the most current regulatory guidance from either the EMA or FDA and includes specific recommendations regarding switch studies. It suggests that margins in the neighbourhood of 4% are clinically tolerable, with typical observed rates of virological failure ranging from 1 to 3%.

As this study (201585) and study 201584 are not sufficiently powered to rule out 4% virologic failure in excess, the 6% margin chosen in each study can be viewed as defining criteria for assessing the consistency acceptability of the study-specific results prior to integration of the studies in the pooled analysis. Assuming an observed control failure rate of 2%, then non-inferiority would be shown in an individual study using a 6% margin if the observed CAB LA+RPV LA failure rate was less than 5% (that is, if the observed treatment difference was less than 3 percentage points). Accordingly, if the individual studies are successful in ruling out a 6% margin, the observed results are expected to be similar and reasonable to integrate for the purposes of the primary efficacy assessment based on the pooled analysis. In addition, a virologic failure rate in this range may be clinically tolerable given the CAB LA + RPV LA regimen may offer important advantages over standard 3-drug oral regimens such as better tolerability, as well as improved adherence and treatment satisfaction in virologically suppressed subjects. Therefore, 6% is considered to be a reasonable non-inferiority margin for the individual studies, with a more stringent 4% margin applied for the pooled analysis.

### 9.2.1.2. Assumption for Virologic Failure Rate at Week 48 (Primary Endpoint)

#### 9.2.1.2.1. Control Arm

The control arm will be comprised of participants whose viral load at time of randomization is suppressed (<50 c/mL) on INI-, NNRTI- or PI- based regimens. Based on these data, reasonable assumptions for the true failure rates are 2% for the control arm and 3% for the CAB + RPV LA injectable regimen.

[Table 9](#) shows the Snapshot response and failure rates observed in five recent stable switch studies. [Table 10](#) shows the difference in snapshot failure rates between Week 48 and Week 96 observed in recent treatment naive studies with INI-based regimens. These differences provide an approximate predication of the failure rates that may be seen in early switch studies enrolling virologically suppressed participants after 48 weeks of initial ART therapy. Taken together, these data suggest that a reasonable assumption for the true failure rate for the current ART control arm is 2%.

**Table 9 Snapshot Analysis Outcomes in Recent Stable Switch Studies**

Week 48			
Study	Treatment Arm	HIV-1 RNA <50	Virologic Failure
SPIRIT a,b	RPV/FTC/TDF	89%	8/317 (2.5%)
STRATEGY-PI c	QUAD	94%	2/290 (<1%)
	PI + FTC/TDF	87%	2/139 (1%)
STRATEGY-NNRTI d	QUAD	93%	3/290 (1%)
	NNRTI + FTC/TDF	88%	1/143 (<1%)
GS-292-0109 e	E/C/F/TAF	97%	10/959 (1%)
	TDF-based regimen f	93%	6/477 (1%)
Week 24			
STRIIVING	DTG + ABC/3TC STR	85%	1%
	Current ART	88%	1%

- a. Participants in the PI/r +2 NRTIs arm were switched to RPV/FTC/TDF at Week 24 and therefore Week 48 response data are not available.
- b. [Palella, 2014]
- c. [Arribas, 2014]
- d. [Pozniak, 2014]
- e. [Martinez, 2010]
- f. E/C/F/TDF or EFC/FTC/TDF or ATV+ FTC/TDF

**Table 10 Snapshot Virologic Failure Rates with INI-based Regimens in Treatment Naive Participants**

Study	Regimen	Week 48	Week 96	Change
SINGLE	DTG/ABC/3TC	21/414 (5%)	42/414 (10%)	+5%
SPRING-2	DTG + ABC/3TC or TDF/FTC	20/411 (5%)	22 /411 (5%)	+0.5%
FLAMINGO	DTG + ABC/3TC or TDF/FTC	15/242 (6%)	19/242 (8%)	+2%
236-0102	E/C/F/TDF	25/348 (7.2%)	6%	-1%
236-0103	E/C/F/TDF	19/353 (5.4%)	24/353 (6.8%)	+2%
292-0104/0111	E/C/F/TAF	4%	5%	+1%
	E/C/F/TDF	4%	4%	0%

**9.2.1.2.2. CAB LA + RPV LA arm**

To inform the failure rate for the CAB LA + RPV LA arm, the Snapshot virologic failure rates from the Phase IIb CAB studies are displayed in [Table 11](#) for the Intent-to-Treat Exposed population. Eligible participants included in the ITT-ME population had HIV-1 RNA <50 c/mL prior to receiving maintenance therapy at Day 1 for LATTE-2 and Week 24 for LATTE.

For LATTE, 9% (7%, excluding 1 participant classified as failure due to ART changes during the induction period) of participants previously suppressed at Week 20 to Week 24 were classified as virologic failures at Week 72 (48 weeks of maintenance treatment with oral CAB + RPV). For LATTE-2, 4% of participants randomized to CAB LA + RPV LA regimens (pooled) were classified as virologic failures after 48 weeks of maintenance treatment. Furthermore, while the failure rate was <1% at Week 48 for Q4W, there was noted variation in the snapshot failure rate over time, ranging between 0% to 3.5% through Week 48, for Q4W. These results suggests a conservative assumption for the true failure rate for the CAB LA + RPV LA Q4W arm of 3%, even

though there is no clinical rationale to suggest that the failure rate is truly higher for the CAB regimen compared to the control regimen.

**Table 11 Snapshot Analysis Outcomes for Phase IIb CAB Studies (Intent-to-Treat Maintenance Exposed Population)**

Week 48			
Study	Maintenance Treatment Arm	HIV-1 RNA <50	Virologic Failure
LATTE-2 (ITT-ME) a	CAB LA + RPV LA Q8W (N=115)	92%	8/115 (7%)
	CAB LA + RPV LA Q4W (N=115)	91%	1/115 (<1%)
	Oral CAB + 2NRTIs (N=56)	89%	1/56 (2%)
	Pooled LA	92%	6/230 (4%)
Week 72			
LATTE (ITT-ME) b	Oral CAB 30mg + RPV (n=53)	83%	9% c

- Participants had HIV-1 RNA <50 c/mL at Week -4 and received oral CAB 30mg + 2 NRTIs as initial induction period therapy from Week -20 to Day 1.
- Participants had HIV-1 RNA <50 c/mL at Week 20 and switched from oral CAB 30mg + 2 NRTIs to Oral CAB 30 mg + RPV at Week 24.
- Includes one participant (2%) that was a virologic success but was classified as failure due to background ART change that occurred during the induction period, which is not an applicable failure category for the CAB LA + RPV LA regimen

### 9.2.1.3. Assumption for Response Rate at Week 48 (Secondary Endpoint)

Given the response rates shown in [Table 9](#) and [Table 11](#), a reasonable assumption for the true success response rate (HIV-1 RNA <50 c/mL) for both arms is 87%.

### 9.2.2. Sample Size Sensitivity

[Figure 8](#) shows the sensitivity of the power curve for the primary comparison to different assumed 'true' virologic failure rates with 285 randomized per arm. Even if the failure rates were 3% for CAB LA + RPV LA and 1% for the control arm, the study will still have over 92% power to meet its primary objective.

[figure not shown]
**Figure 8 Sensitivity of Estimated Power for Snapshot Virologic Failure**

Table 12 shows the power with 285 randomized per arm and the sample size required to guarantee 90% power, for a range of ‘true’ virologic failure rates. For instance, even if the failure rates were 3% for CAB LA + RPV LA and 1% for the control arm, the study will still have over 92% power to meet its primary objective with the planned sample size. However, if the failure rates were 4% for CAB LA + RPV LA and 2% for control, an additional ninety-six participants per arm would be required to obtain 90% power for the primary treatment comparison.

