## 4. STUDY DESIGN

### 4.1. Overall Design

201585 (ATLAS) is a Phase III, randomized, open-label, active-controlled, multicenter, parallel-group, non-inferiority study designed to assess the antiviral activity and safety of a two drug regimen of CAB LA + RPV LA compared with maintenance of current ART. Approximately 570 adult HIV-1 infected patients who are on a stable ARV regimen containing 2 NRTIs plus an INI, NNRTI, or a PI will be randomized 1:1 to continue current ART or be switched to the CAB LA + RPV LA regimen through 52 weeks. The study will continue with an Extension Phase up to at least 96 weeks.

Participants will be randomized (1:1) at Day 1 to either continue on current ART or to discontinue current ART and begin oral therapy with CAB 30 mg + RPV 25 mg once daily to determine individual safety and tolerability, prior to administration of CAB LA + RPV LA. Current ART dosing on Day 1 is recommended to occur after randomization to avoid overlap of regimens (in the event that the participant is assigned to the CAB LA + RPV LA treatment arm). However, if the participant takes current ART prior to coming into the clinic, randomization and initiation of oral CAB and RPV should continue as planned for Day 1.

For those randomized to receive CAB + RPV, at the Week 4a visit safety assessments (including e.g., clinical chemistries) will be performed as per the Time and Events Table (Section 7.1). At visit Week 4b, participants will return to the clinic, take the last dose of oral CAB + RPV, and receive the first CAB LA (600 mg) + RPV LA (900 mg) injections (within 2 hours of the final oral dose of CAB + RPV). The first injection visit (Week 4b) can be performed once central lab results are available and safety parameters are reviewed. If a retest is required based on Week 4a labs, the retest should be performed as soon as possible (and preferably no later than 7 days following Week 4a). Participants will remain on oral CAB 30 mg + RPV 25 mg until the Week 4b injection visit, and until any required Visit 4a retest results are available for review. The visit schedule following the oral lead-in phase will be based on timing of the first injection visit at Week 4b such that the Week 5 visit should be performed approximately 7 days after the Week 4b visit.

[figure not shown]

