**Table 12 Sensitivity of Estimated Power for Snapshot Virologic Failure**

Control Arm Virologic Failure Rate (%)	CAB LA + RPV LA Arm Virologic Failure Rate (%)	6% Non-inferiority Margin	
		Power (%) with N=285 per arm	N Required per arm for 90% Power
1%	1%	>99.9%	73
1%	2%	99.8	124
1%	3%	92.7	257
1%	4%	63.4	564
1.5%	1.5%	>99.9%	98
1.5%	3%	95.2	228
2%	2%	>99.9%	115
2%	2.5%	99.3	153
2%	3%	96.8	205
2%	3.5%	90.8	277
2%	4%	80.0	381
3%	3%	98.7	170
3%	4%	90.1	284

Table 13 show the sensitivity of the estimated sample size and power for the secondary endpoint comparison of response rates (HIV-1 RNA <50 c/mL at Week 48) to different assumed 'true' response rates.

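### The stated power of over 92% at true failure rates of 3% vs 1% is a normal approximation; the planned type of interval gives about 89%, and most of Table 12's sample sizes fall short of 90%

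*Protocol*

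**What the plan says.** Section 9.2.1 fixes the design inputs: "This study will randomize approximately 285 participants per arm", with "a non-inferiority margin of 6%, and a 2.5% one-sided significance level". At the base case of 3% vs 2% it says "this would provide approximately 97% power to show non-inferiority".

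Section 9.2.2 then tests sensitivity. Before Figure 8 it says of 3% vs 1% that "the study will still have over 92% power to meet its primary objective". After Figure 8 it repeats the claim for the same pair of rates, now as an example drawn from Table 12: "the study will still have over 92% power to meet its primary objective with the planned sample size". Table 12 gives 92.7% for this row. Its last column, "N Required per arm for 90% Power", gives 257. The text introducing the table describes that column as the size that will guarantee 90% power.

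Section 9.4.1 defines success: the upper end of a two-sided 95% confidence interval for the difference in failure rates must lie below 6%. The interval is a CMH-weighted difference with the Sato variance, stratified by third-agent class and gender at birth. Section 9.2 does not say by what method the power figures were computed.

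**The concern.** At a 1% control rate, 285 participants yield 2.85 expected failures. The count is small, discrete and skewed. When few control failures occur, the observed difference tends to be larger and the tolerance for failures on the new regimen smaller, in a way that a normal curve does not capture. A power figure from the normal approximation can then differ from what the planned interval delivers.

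At stake is whether a sensitivity statement, made twice and without qualification, is true of the design, and whether a sample size described as guaranteeing 90% power does so. The 3% vs 1% row is the one the text singles out for reassurance, and the correction takes it from above 90% to below.

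**Working it through.** **Inputs.** 285 per arm, 1:1, margin 0.06, one-sided 2.5% (Sections 4.1 and 9.2.1); true rates 3% and 1% (Section 9.2.2); success if the 95% upper limit is below 6% (Section 9.4.1).

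**1. Reproducing the protocol's figure.** Unpooled normal approximation:

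- SE = √[(0.03×0.97 + 0.01×0.99)/285] = √(0.0390/285) = 0.01170
- Power = Φ[(0.06 − 0.02)/0.01170 − 1.96] = Φ(3.419 − 1.960) = Φ(1.459) = 92.8% (printed 92.7%)
- N for 90% = (1.960 + 1.282)² × 0.0390/0.04² = 10.507 × 24.375 = 256.1, so 257 (printed 257)

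All 13 power cells in Table 12 reproduce within 0.1 point this way, and 11 of the 13 sample-size cells reproduce exactly.

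**2. Exact power at 285 per arm.** With x failures on CAB LA + RPV LA and y on control, success means x/n − y/n + 1.96 × √[p₁(1−p₁)/n + p₂(1−p₂)/n] < 0.06, where p₁ = x/n and p₂ = y/n. For each y, find the largest x that still succeeds, and sum over both binomial distributions:

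| y | P(y), rate 1% | largest x | P(X ≤ x), rate 3% |
|---|---|---|---|
| 0 | 0.0570 | 10 | 0.7603 |
| 1 | 0.1641 | 11 | 0.8476 |
| 2 | 0.2354 | 11 | 0.8476 |
| 3 | 0.2243 | 12 | 0.9093 |
| 4 | 0.1598 | 13 | 0.9493 |
| 5 | 0.0907 | 13 | 0.9493 |
| 6 | 0.0428 | 14 | 0.9734 |
| 7 | 0.0172 | 15 | 0.9868 |
| 8 | 0.0060 | 15 | 0.9868 |

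The products sum to 0.888. The remaining y (probability about 0.003) bring the total to 0.891, so exact power is **89.1%**, or 92.7 − 89.1 = 3.6 points below the printed value. Simulating the six-stratum CMH/Sato interval gives 89.0% to 89.2%. That rests on assumptions the protocol does not fix: third-agent shares of 40/40/20 or 35/50/15 and 25% women.

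**3. Exact power at the printed sample sizes.** The same enumeration at the N of each row that follows the approximation:

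| Control / CAB LA + RPV LA | printed N | exact power |
|---|---|---|
| 1% / 2% | 124 | 86.0% |
| 1% / 3% | 257 | 87.6% |
| 1% / 4% | 564 | 87.8% |
| 1.5% / 3% | 228 | 87.2% |
| 2% / 2% | 115 | 89.1% |
| 2% / 2.5% | 153 | 87.6% |
| 2% / 3% | 205 | 88.3% |
| 2% / 3.5% | 277 | 88.6% |
| 2% / 4% | 381 | 88.2% |
| 3% / 3% | 170 | 89.9% |
| 3% / 4% | 284 | 89.5% |

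None reaches 90%. The 2%/4% row is behind the sentence on ninety-six additional participants per arm (381 − 285 = 96). For 1%/3%, exact power first passes 90% at 287 per arm. Because it moves in a sawtooth, it stays above 90% only from 295.

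**4. The two odd cells.** For 1%/1% and 1.5%/1.5% the approximation gives N of 58 and 87; the table prints 73 and 98. Searching upward from 58 and 87, exact power first reaches 90% at exactly 73 (85.8% at 72, 90.1% at 73) and 98 (87.5% at 97, 91.4% at 98).

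**5. Other stated figures, printed vs exact.** Base case 2%/3%: 96.8% vs 95.5%. Row 1.5%/3%: 95.2% vs 92.9%. Row 2%/3.5%: 90.8% vs 89.1%. Pooled analysis (570 per arm, 4% margin): 90% vs 89.0%.

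**The case against.** The strongest reply is that nothing was miscalculated. The unpooled normal approximation is a standard planning method, the printed 92.7% and 257 follow from it, and table and figure are both titled as estimated power. That stands: a reader might infer an arithmetic slip, and the reproduction above rules it out. It explains where the number came from, however; it does not make the number true of the planned interval, and the text states it without qualification.

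A reader might also infer that mixed methods produced the 92% figure. They did not. The mixing touches two sample-size cells and no power cell, and both cells are larger than the approximation would give. Their origin is inferred: the match depends on searching upward from the approximate N, and for 1%/1% exact power dips just below 90% again at 74 to 78.

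Nor is 3% vs 1% the headline scenario. The headline is 3% vs 2%, which moves little. The control arms with counts in Table 9 total (2 + 1 + 6)/(139 + 143 + 477) = 9/759 = 1.2%, which makes a 1% control rate plausible. But Section 9.2.1.2.2 calls 3% for the new regimen conservative, and Table 11 shows 1/115 on Q4W dosing. The row is an unfavourable stress case, not the protocol's best guess for both arms.

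**Conclusion.** The point holds as a matter of accuracy. At 3% vs 1% the planned type of limit has about 89% power, not over 92%, and the N column does not guarantee 90% in any of the eleven approximation-based rows (about 86% to 90% exact). The 89.1% rests on the unstratified, unpooled 95% limit. Agreement with the stratified interval depends on assumed strata shares, but barely moves with them.

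The documents do not support reading this as an underpowered trial. Base-case and pooled power fall by about 1 point. The sample size was chosen mainly for the pooled analysis (Section 4.1). Margin, error rate and decision rule are untouched, and 89% in a stress case still leaves the study well powered.

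**What to change.** Recompute Table 12 and Figure 8 by one method and name it: exact enumeration, or simulation of the planned CMH/Sato interval with the assumed strata shares stated. In Section 9.2.2 replace the over-92% statement with about 89% in both places, and update the sentence on ninety-six additional participants. Correct the N column or drop the claim that it guarantees 90%. If exact values are used, say whether N is the first size to reach 90% or the size from which power stays there (287 vs 295 for 1%/3%).

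Optionally, note in Section 9.2.1 and the synopsis that the base-case and pooled figures are about 95.5% and 89% by the exact method.

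The cost is one rerun table and figure and a few edited sentences, with stated powers up to about 4 points less favourable. Enrolment does not change.

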**Table 12 Sensitivity of Estimated Power for Snapshot Virologic Failure**

Control Arm Virologic Failure Rate (%)	CAB LA + RPV LA Arm Virologic Failure Rate (%)	6% Non-inferiority Margin	
		Power (%) with N=285 per arm	N Required per arm for 90% Power
1%	1%	>99.9%	73
1%	2%	99.8	124
1%	3%	92.7	257
1%	4%	63.4	564
1.5%	1.5%	>99.9%	98
1.5%	3%	95.2	228
2%	2%	>99.9%	115
2%	2.5%	99.3	153
2%	3%	96.8	205
2%	3.5%	90.8	277
2%	4%	80.0	381
3%	3%	98.7	170
3%	4%	90.1	284

Table 13 show the sensitivity of the estimated sample size and power for the secondary endpoint comparison of response rates (HIV-1 RNA <50 c/mL at Week 48) to different assumed 'true' response rates.

**Table 13 Sensitivity of Estimated Power for Snapshot Virologic Success**

Control Arm Virologic Success Rate (%)	CAB LA + RPV LA Arm Virologic Success Rate (%)	-10% Non-inferiority Margin	
		Power (%) With N=285	N Required per arm for 90% Power
85%	85%	91.6	268
86%	85%	86.2	322
86%	86%	93.0	254
86%	87%	97.0	203
87%	85%	78.6	396
87%	86%	88.1	303
87%	87%	94.4	238
87%	88%	97.7	190
88%	87%	90.1	284
88%	88%	95.6	222
88%	89%	98.4	177
89%	89%	96.8	206

### 9.2.3. Sample Size Re-estimation or Adjustment

No sample-size re-estimation based on response data is planned for this study.

### **9.3. Data Analysis Considerations**

#### **9.3.1. Analysis Populations**

##### **9.3.1.1. Intent-to-Treat Exposed (ITT-E)**

The ITT-E population will consist of all randomly assigned participants who receive at least one dose of study drug. Participants will be assessed according to their randomized treatment, regardless of the treatment they received. The population used in the primary efficacy analysis will be the ITT-E population.

##### **9.3.1.2. Per-Protocol Population (PP)**

The Per-Protocol (PP) Population will consist of all participants in the ITT-E Population with the exception of major protocol violators. The PP will be used for sensitivity analysis of the primary endpoint.

##### **9.3.1.3. PK Population**

The PK Population will include all participants who receive CAB and / or RPV and undergo PK sampling during the study, and provide evaluable CAB and /or RPV plasma concentration data. Participants in this population will be included in the PK analysis.

##### **9.3.1.4. Safety Population**

The Safety Population will consist of all randomly assigned participants who receive at least one dose of study drug. Participants will be assessed according to actual treatment received. Unless otherwise stated, the Safety Population will be used for safety analyses.

#### **9.3.2. Treatment Comparisons**

##### **9.3.2.1. Primary Comparison of Interest**

The primary analysis will be based on the ITT-E population using the Snapshot dataset. The primary comparison will be made at a one-sided 2.5% level of significance. Treatment with CAB LA + RPV LA will be declared non-inferior to current ART if the upper end of a two-sided 95% confidence interval for the difference between the two groups (CAB – current ART) in virologic failure rates at Week 48 lies below 6%.

